15.1.2 Adverse Events Leading to Treatment Discontinuation

The following overall frequency tables will be prepared for the adverse event actions. Tables will be provided by PT and primary SOC in alphabetical order:

- Any AE leading to temporary discontinuation of study drug,
- Any AE leading to permanent discontinuation of study drug,
- Any AE leading to dose reduction of study treatment.

15.2 Deaths, Other Serious Adverse Events, and Other Significant Adverse Events

15.2.1 Deaths

Any discontinuations due to death (see Section 10.1) and any AE leading to death will be tabulated (see Section 15.1.1).

A summary table of observed Deaths (from “Study Termination” eCRF page) will be provided together with TEAEs with fatal outcome by PT.

15.2.2 Serious Adverse Events

The statistical analysis and reporting of serious adverse events are defined in Section 15.1.1. In addition, all serious adverse events will be listed.

15.2.3 Other Significant Adverse Event

TEAEs associated to COVID-19

The frequency of TEAEs associated to COVID-19 will be presented. The relevant events will be identified based on the SMQ COVID-19 (narrow scope) and will be presented by SOC and PT.

Fatigue

The prevalence of fatigue will be presented for each month of the Course 1 Treatment Period and separately for each month of the Course 2 Treatment Period. The prevalence at a given month is defined as:

(Number of subjects with fatigue during the month/ Number of subjects with fatigue during the month or still in the study at the end of the month) * 100,
where subjects with fatigue during the month are all subjects who had at least one reported TEAE with PT equal to 'Fatigue' that either started during the month or is still ongoing from the previous month.

If the end date of the AE is partially or completely missing and the AE is not reported as ongoing, the end date will be imputed as follows:

- Day missing but month and year available: last day of the month,
- Day and month missing: last day of the year but not later than end of Treatment Period 2,
- Completely missing: end of Treatment Period 2

The results will be presented in a tabular as well as graphical manner. Course 1 and 2 Treatment Periods as well as duration of a month is defined in Section 9.

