- Period 100.1 (p_{100.1}) is defined as the Period between Baseline and Month 1 MRI scans,

- Period 100.2 (p_{100.2}) is defined as the Period between Month 1 and Month 2 MRI scans,
- Period 100.3 (p_{100.3}) is defined as the Period between Month 2 and Month 3 MRI scans,
- Period 100.6 (p_{100.6}) is defined as the Period between Month 3 and Month 6 MRI scans,
- Period 100.12 (p_{100.12}) is defined as the Period between Month 6 and Month 12 MRI scans,
- Period 100.15 (p_{100.15}) is defined as the Period between Month 12 and Month 15 MRI scans,
- Period 100.18 (p_{100.18}) is defined as the Period between Month 15 and Month 18 MRI scans,
- Period 100.24 (p_{100.24}) is defined as the Period between Month 18 and Month 24 MRI scans.

Note: Period start and end dates are defined by the MRI dates as provided by central reading.

Definition of change from Baseline

Change from Baseline = Visit value – Baseline value.

Percentage Change from Baseline = $100 \times (\text{Visit value} - \text{Baseline value}) / \text{Baseline value}$.

The Percentage Change from Baseline will be set to missing for subjects with a zero at Baseline.

Definition of Visit dates

The Visit start date is the date of the first assessment which belongs to the corresponding Visit.

The Visit end date is the date of the last assessment which belongs to the corresponding Visit.

Definition of duration

Duration will be calculated by the difference of start and stop date + 1, in days (unless specified otherwise).

Treatment Period

The treatment Period begins with the start of study medication on Study Day 1 and continues through to the completion of the treatment Period at the Month 24 Visit (see CSP, Section 7.1.2). Start of study medication is the date of first intake of study medication. Start of study medication in Year 2 is the date of first intake of study medication at or after the Month 12 Visit.

Treatment Period:

- Start = Start of study medication,
- End = Visit end date of Month 24 Visit, or Early Termination (ET) Visit, in case of early discontinuation, or the study discontinuation date, if the ET Visit was not performed.

Course 1 Treatment Period:

- Start = Start of study medication,

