- End = Start of study medication at or after the Month 12 Visit - 1 day, or if the subject did not receive Treatment Course 2: Start of study medication of Treatment Course 1 + 457 days (which is obtained by 360 (12 months) + 90 (3 months) + 7 (Visit window)) or date of discontinuation, if earlier.

Course 2 Treatment Period:

- Start = Start of study medication at or after the Month 12 Visit,
- End = End of Treatment Period.

Definition of Delayed Treatment Course 2

The Treatment Course 2 will be defined as delayed, if the start of study medication is delayed by more than 3 months (= 90 days) or did not start at all i.e.:

- Start of Study medication of Treatment Course 2 > Start of Study Medication of Treatment Course 1 + 457 days (which is obtained by 360 (12 months) + 90 (3 months) + 7 (Visit window)), or
- Treatment Course 2 never started (i.e., no study medication taken at or after the Month 12 Visit).

Data handling in case of a Delayed Treatment Course 2

For subjects with a Delayed Treatment Course 2, only data observed during the Course 1 Treatment Period will be analyzed in all efficacy analyses. Efficacy data after the Course 1 Treatment Period will be counted as missing in the statistical analyses and marked in the listings. In all efficacy analyses defined by Period, the subject will be classified as if the subject discontinued at the end of the Course 1 Treatment Period. For subjects without a delay the whole Treatment Period will be analyzed.

For all other analyses (except efficacy) the data is not limited to the Course 1 Treatment Period for subjects with a Delayed Treatment Course 2.

Definition of start of COVID-19-Pandemic

The start of COVID-19 pandemic will be defined by country as the earliest date of either the date of the first death from COVID-19 occurred in each country according to the published data by European Centre for Disease Prevention and Control on 26th June 2020 (<https://www.ecdc.europa.eu/en/publications-data/download-todays-datageographic-distribution-covid-19-cases-worldwide>) or 11th March 2020 (when the WHO declared COVID-19 pandemic).

Visit timing with respect to COVID-19 pandemic

A Visit is defined to be performed after the start of COVID-19 pandemic if the Visit end date is greater than the start of COVID-19 pandemic date.

Conversion factors

The following conversion factors will be used to convert days into months or years for all observations except Visit related dates:

- 1 month = 30.4375 days,

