- 1 year = 365.25 days.

Time window

- Day 1 is the day of start of study medication, the day before is Day - 1 (no Day 0 is defined),
- Study day / Treatment day is defined relative to Day 1.

The Visit schedule is defined as follows:

- 1 month = 30 days,
- 1 year = 360 days,

relative to the start date of the Baseline Visit for Treatment Course 1 and relative to the start date of the Month 12b Visit as defined in the eCRF (see also Section 15.3) for Treatment Course 2.

In each analysis, should assessments be delayed, subjects' assessment data will be treated as though it occurred at the time point specified (i.e., out of Visit windows will be not excluded or adjusted for any analyses) and inferences will be conducted accordingly. Thus, further time windows will not be specified.

All observations from unscheduled Visits will be included only in the analyses of Visit independent summaries (e.g. counts of events, progressions or worst value during Treatment Period) unless for the unscheduled Visits prior to start of study medication and the last assessment available. In case of unscheduled Visits prior to start of study medication, these will be considered to define Baseline. In the last missing case the ET Visit will be imputed by the unscheduled Visit.

The assessments of the ET Visit will be mapped to the nearest planned post-Baseline Visit with a missing assessment before or after the ET Visit of the individual assessment for all statistical analyses and descriptive summaries. As not all assessments of the ET are performed at each Visit, the different assessments of the ET can be assigned to different Visits. If the duration (in days) between the ET Visits and two missing planned Visits are equal, then the assessment will be assigned to the later Visit.

Handling of missing data

Unless otherwise specified in respective sections, missing data will not be replaced.

The handling of missing covariate and stratification factor information is described below.

The handling of missing DMD end date is described in Section 12.

Incomplete or missing onset dates of relapses from "MS Relapse Report" will be imputed as follows:

- In cases where the onset date is partially missing but the onset month and year, or the onset year are equal to the start of study medication or the date is missing then the onset date will be replaced by the start date of study medication.

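### The monthly fatigue prevalence drops fatigue-free subjects who leave during a month but keeps those with fatigue, so it is overstated in the last month or months of Course 2, when completers leave on schedule

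*SAP*

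**What the plan says.** SAP 15.2.3 (Fatigue) plans a prevalence for each month of Course 1 and "separately for each month of the Course 2 Treatment Period", shown as a table and a graph. The numerator is every subject with a fatigue event "that either started during the month or is still ongoing from the previous month". The denominator is "Number of subjects with fatigue during the month or still in the study at the end of the month".

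For the calendar the section refers elsewhere: "Course 1 and 2 Treatment Periods as well as duration of a month is defined in Section 9". Section 9 contains the following.

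- Conversion factors: "The following conversion factors will be used to convert days into months or years for all observations except Visit related dates", followed by "1 month = 30.4375 days".
- Visit schedule: 30-day months and "1 year = 360 days", counted for Course 2 from the start of the Month 12b Visit.
- Treatment Period, which also closes Course 2: "End = Visit end date of Month 24 Visit, or Early Termination (ET) Visit".

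Protocol 7 and 7.1.12 make Month 24 the final visit, with a window of ± 7 days. Neither document gives a rule for the last or a partial month of the fatigue display.

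**The concern.** Entry into the denominator depends on the outcome. A subject with fatigue counts in the numerator and the denominator even if observed for one day of the month. A fatigue-free subject who leaves on the same day counts in neither. The ratio is therefore too high in any month in which fatigue-free subjects leave.

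This would not matter if exits were rare and scattered. At the end of Course 2 they are neither, because every completer is scheduled to leave within about two weeks, close to the end of month 12. The graph would then show a rise in fatigue about a year after the second course that comes from the formula. The trial has a single arm, so no control curve would show the same rise and reveal the artefact.

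**Working it through.** The documents state no expected fatigue rate, so there is no planned figure to reproduce. The SAP's delay limit, 360 + 90 + 7 = 457 days, confirms that its visit calendar uses 30-day months.

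**Inputs**

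- Exit of completers: Month 24 Visit 360 days after Month 12b (SAP 9). Assuming the first Course 2 dose is taken on the Month 12b date, this is Course 2 day 361. With ± 7 days it is day 354 to 368, which is 15 possible days.
- End of Course 2 month 12: 12 × 30.4375 = day 365.25 with the conversion factor for non-visit data, or 12 × 30 = day 360 with the visit calendar.
- True prevalence p in the month: not given. Assumed 5% and 10%, with 2% and 20% as the range.
- Visit dates: distribution not given. Assumed uniform over the 15 days, then varied.

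**Formula.** Let r be the share of fatigue-free subjects still in the study at month end. Then

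reported prevalence = p / (p + (1 − p) r), and the inflation factor is 1 / (p + (1 − p) r), which cannot exceed 1/p.

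**Share still in the study**

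- 30.4375-day month: visits on days 366 to 368, so r = 3/15 = 0.20. If a visit on day 365 is also counted as still in, r = 4/15.
- 30-day month: visits on days 361 to 368, so r = 8/15 = 0.53.

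**Results for month 12**

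| True p | r = 3/15 | r = 8/15 |
|---|---|---|
| 2% | 9.3% (4.6×) | 3.7% (1.8×) |
| 5% | 0.05/(0.05 + 0.19) = 20.8% (4.2×) | 0.05/(0.05 + 0.507) = 9.0% (1.8×) |
| 10% | 0.10/(0.10 + 0.18) = 35.7% (3.6×) | 0.10/(0.10 + 0.48) = 17.2% (1.7×) |
| 20% | 55.6% (2.8×) | 31.9% (1.6×) |

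With r = 4/15, a true 5% is reported as 0.05/(0.05 + 0.253) = 16.5%.

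**Visit spread (30.4375-day month).** If visits cluster normally around day 361 with SD 3.5 days, r = 0.10 and the factor is 6.9 at p = 5% and 5.3 at p = 10%. With SD 5 days, r = 0.18 and the factors are 4.4 and 3.8.

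**In counts.** Take the planned 265 subjects, 13 of them with fatigue (13/265 = 4.9%). Of the 252 without fatigue, about 50 are still in at r = 0.20, so the SAP formula gives 13/(13 + 50) = 20.6%.

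**Later partial month.** Under either month length the late visits run into month 13, which ends at day 395.7 or 390. If all visits fall within the window, nobody remains at its end. The denominator is then the subjects with fatigue alone, and the result is 100% if there is any fatigue.

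**Ordinary months.** With an assumed 10% to 20% dropout over 24 months, monthly loss is 0.4% to 0.9% and the inflation factor is only 1.004 to 1.009.

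**The case against.** The strongest reply is that the months belong to the Course 2 Treatment Period, which ends for each completer at the Month 24 Visit. A programmer could therefore treat a completer as in the study through his or her last month, and the inflation would vanish. That is a sensible convention, but the SAP does not state it, and its wording requires presence at the end of the month.

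Two further points limit the size. Section 9 gives two month lengths, and the shorter one brings the factor below 2. The exit date is the end date of the visit, and Protocol 7 and 7.3.2 allow assessments to be split by ± 5 days. Last assessments falling 3 days later on average (assumed) would give r = 6/15, so a true 5% would be reported as 0.05/(0.05 + 0.38) = 11.6%. Both points stand as limits on the size. Neither removes the bias.

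It is also true that little rests on this display. It describes one preferred term, with no test or decision attached. The adverse event frequencies, exposure-adjusted incidence rates and subject listing in SAP 15.1.1 are unaffected.

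A reader might also infer a false fall in prevalence late in Course 1, since most subjects have by then moved to Course 2 but are still in the study. The documents do not support this. It needs a numerator limited to subjects still in Course 1 and a denominator that is not. The formula itself restricts neither part to a Course, and a reading that takes the restriction from the preceding sentence would apply it to both.

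**Conclusion.** The denominator is wrong as stated, and the error matters in the last month or months of Course 2. With uniform visit dates, a true 5% or 10% appears as about 21% or 36% under 30.4375-day months, the length that Section 9 assigns to non-visit data, and as about 9% or 17% under 30-day months. A later partial month shows 100% if any fatigue occurs and no one remains at its end.

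These figures rest on an assumed prevalence, an assumed spread of visit dates and a Course 2 start on the Month 12b date. It would go too far to say that the plan fixes a several-fold error, because the factor is not determined by the documents. Earlier months are essentially sound, and the primary analysis is untouched. The correction is still worth making, because the artefact would appear in the graph as a late safety signal.

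**What to change.** In SAP 15.2.3, define the denominator as all subjects in the safety analysis set with at least one day of the given Course Treatment Period in that month, with or without fatigue. Restrict the numerator to the same subjects and the same Course. State that the 30.4375-day month of Section 9 applies. In the example above, the last month then returns 13/265 = 4.9%.

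Alternatively, end the Course 2 display at the last full month before the Month 24 window opens on day 354. With 30.4375-day months that is month 11, which ends at 11 × 30.4375 = day 334.8. This leaves the small asymmetry in earlier months.

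The cost is about one sentence in the SAP and a small programming change, with no new data. The downside of the new denominator is that subjects observed for part of a month count as full subjects, which lowers the figure slightly.

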15.3 Clinical Laboratory Evaluation

Lymphocyte counts from local laboratory will be used for summary statistics and shift tables. They will be classified according to the NCI-CTCAE. The classification will be derived only from the laboratory results at a given assessment, thus ignoring the underlying syndrome.

The Treatment Course 2 can be delayed because of Lymphocyte count below 800 cells/mm³ at the Month 12 Visit. In this case, the Lymphocyte count can be measured several times between the Month 12 Visit and the start of Treatment Course 2. Lymphocyte counts at or after the Visit start date of the Month 12 Visit and before or at the start date of the Treatment Course 2 will be displayed as followed:

- The earliest Lymphocyte count will be assigned to the Month 12 Visit,
- The latest Lymphocyte will be assigned to the Month 12b Visit,
- All other Lymphocyte count will be assigned to unscheduled Visits.

A Lymphocyte count can be assigned to the Month 12 Visit and Month 12b Visit if just one count is available. If the Treatment Course 2 wasn't started, only the earliest Lymphocyte count will be assigned to the Month 12 Visit.

The worst on-study grade (i.e., on, or after, first study treatment administration) will be summarized by subject considering only subjects with post-Baseline laboratory samples: Laboratory tests by NCI-CTC grade (0, 1, 2, 3, 4, any).

Lymphocyte counts will be examined for trends using descriptive statistics (mean, SD, median, Q1, Q3, minimum, and maximum) of actual values and changes from Baseline to each scheduled Visit including Month 12b Visit over time. If for a particular Visit a different local laboratory than normal laboratory was used (due to COVID-19 pandemic), values collected during that Visit will not be included in the descriptive statistics.

Shift tables of Baseline versus endpoint (as well as the worst value at any post-Baseline Visit) will be presented. Abnormalities classified according to NCI-CTCAE toxicity grading will be described using the worst grade.

All Lymphocyte counts will be listed by subject for the SAF.

Positive results of the tuberculosis and serology tests that do not comply with the protocol will be listed.

15.4 Vital Signs

The maximum changes of vital sign measurements from Baseline to maximum change after start of 1st treatment will be grouped as follows:

Heart rate increase from Baseline <100 bpm; ≥ 100 bpm	≤20 bpm, >20 – 40 bpm, >40 bpm
Heart rate decrease from Baseline <100 bpm; ≥ 100 bpm	≤20 bpm, >20 – 40 bpm, >40 bpm
SBP increase from Baseline <140 mmHg; ≥ 140 mmHg	≤20 mmHg, >20 – 40 mmHg, >40 mmHg
SBP decrease from Baseline <140 mmHg; ≥ 140 mmHg,	≤20 mmHg, >20 – 40 mmHg, >40 mmHg
DBP increase from Baseline <90 mmHg; ≥ 90 mmHg	≤20 mmHg, >20 – 40 mmHg, >40 mmHg
DBP decrease from Baseline <90 mmHg; ≥ 90 mmHg,	≤20 mmHg, >20 – 40 mmHg, >40 mmHg

For each subject, the worst change during the treatment Period will be considered. Missing values will be presented as a separate category.

The following will be prepared for vital sign parameters as grouped above considering only subjects with post-Baseline values:

- Summary of Maximal Shifts (changes in categories),
- Listing of highest change per subject.

18.1 Appendix 1: List of DMDs

DMDs	Preferred Term
Alemtuzumab* (Campath, MabCampath, Lemtrada)	ALEMTUZUMAB
Daclizumab* (Zinbryta)	DACLIZUMAB
Dimethyl fumarate (Tecfidera)	DIMETHYL FUMARATE
Fingolimod* (Gilenya)	FINGOLIMOD FINGOLIMOD HYDROCHLORIDE
Glatiramer Acetate (Copaxone)	GLATIRAMER GLATIRAMER ACETATE
Immunoglobulins	IMMUNOGLOBULIN HUMAN NORMAL IMMUNOGLOBULINS IMMUNOGLOBULINS NOS
Interferon beta (Avonex, Rebif, Betaferon, Extavia, Plegridy)	INTERFERON INTERFERON BETA INTERFERON BETA-1A INTERFERON BETA-1B PEGINTERFERON PEGINTERFERON BETA-1A
Mitoxantrone (Novantrone)	MITOXANTRONE MITOXANTRONE HYDROCHLORIDE
Natalizumab* (Tysabri)	NATALIZUMAB
Non-approved investigational DMDs* (monoclonal antibodies, antiS1PR, laquinimod etc)	DIROXIMEL FUMARATE INVESTIGATIONAL DRUG LAQUINIMOD OFATUMUMAB OPICINUMAB OTHER ANTINEOPLASTIC AGENTS OZANIMOD
Ocrelizumab* (Ocrevus)	OCRELIZUMAB
Off-label immunosuppressants (azathioprine, mycophenolate, cyclophosphamide)	AZATHIOPRINE CYCLOPHOSPHAMIDE METHOTREXATE
Siponimod*	SIPONIMOD
Teriflunomide (Aubagio)	TERIFLUNOMIDE
DMDs marked with a * are second line DMDs, which are not allowed as a previous medication according to the study protocol.	

Subjects who have taking any of the listed DMDs according to the “Relevant Previous Medication” eCRF page will be categorized as DMD pre-treated. All other subjects will be considered as pre-treatment naïve. The list may be extended during medical review in case that new or other DMDs will be applied during the study.

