5.3.2 Exclusion Criteria

To be eligible for inclusion in this study the subjects must not meet any of the following criteria:

1. Previous exposure to drugs such as fingolimod, natalizumab, alemtuzumab, mitoxantrone and ocrelizumab
2. Hypersensitivity to Mavenclad[®] or to any of the excipients listed in the SmPC
3. Lymphocyte count not within normal limits of the local, hospital laboratory before initiation of first treatment course
4. Presence of signs of PML detected by MRI, clinical and/or biomarker evaluations or other (than MS) major Central Nervous System disease clinically diagnosed or evidenced in screening MRI

5. Positive for HIV
6. Positive test for hepatitis C or positive tests for hepatitis B infection: either hepatitis B surface antigen (HBsAg) positive, or positive hepatitis B core antibody (total anti HBcAb) confirmed by a positive viral polymerase chain reaction (PCR). An individual benefit-risk evaluation should be performed before initiating Mavenclad® in non-immune subjects for Hepatitis B and the individual level of risk for HBV infection should be assessed by the Investigator
7. History of active tuberculosis (TB), current diagnosis of active tuberculosis, undergoing current treatment for latent TB infection (LTBI), LTBI as detected by local standard of practise like imaging (e.g., chest X-ray, chest computerized tomography [CT] scan, MRI) and/or positive QuantiFERON-TB Gold test and/or skin test and/or clinical examination
8. Immunocompromised subjects, including subjects currently receiving immunosuppressive or myelosuppressive therapy with, e.g., monoclonal antibodies, methotrexate, cyclophosphamide, cyclosporine, or azathioprine, or chronic use of corticosteroids
9. Active malignancy. An individual benefit-risk evaluation should be performed before initiating Mavenclad® in subjects with prior malignancy. Subjects treated with Mavenclad® should be advised to follow standard cancer screening guidelines
10. Subjects with hereditary problems of fructose intolerance
11. Received a live vaccine within 4 to 6 weeks prior to Mavenclad® administration or intends to receive a live vaccination during the trial. After the last dose of Mavenclad®, the subject should avoid live vaccine as long as the subject's white blood cell counts are not within normal limits
12. Allergy or hypersensitivity to gadolinium and/or any other contraindication to perform an MRI

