8.2 Definition of Analysis Sets and Subgroups

Enrolled Set (ES)

All subjects enrolled in the study, i.e., all subjects with a signed informed consent.

Intent-to-treat Set (ITT)

All subjects classified as eligible (i.e., medication assigned by iRT at the Baseline Visit).

Full Analysis Set (FAS)

All subjects in the ITT treated with at least one dose of study medication.

Treatment Completer Set – Year 1 (TCS-1)

All subjects from the FAS who completed the full Treatment Course of the first year (Treatment Course 1). Subjects will be classified as Treatment Completer for the first year if they have a compliance greater than or equal to 100% for Treatment Course 1.

Treatment Completer Set – Year 2 (TCS-2)

All subjects from the FAS who completed the full Treatment Course of the first and the second year. Subjects will be classified as Treatment Completer for the second year if they have a compliance greater than or equal to 100% for Treatment Course 1 and Treatment Course 2 and received the treatment without delay (see Section 9 for definition).

Safety Analysis Set (SAF)

All subjects treated with at least one dose of study medication.

Unless otherwise specified, all efficacy analyses will be performed on the FAS.

Some tertiary analyses will be repeated on the Treatment Completer Sets and the primary analysis, on the ITT (if different from FAS), to evaluate the robustness of the primary results to deviations of the planned treatment regimen. Further details are given in the respective sections. All safety analyses will be performed on the SAF.

Additional Subgroup or Subset Analysis Sets

Subgroup analyses will be performed on subgroups as defined below.

- High-relapse activity (HRA)
 - HRA: at least 2 relapses in the previous year (i.e. the number of historical relapses within 12 months prior to Baseline ≥ 2) regardless of prior use of DMDs
 - Non-HRA: otherwise

Unless otherwise indicated, all descriptive statistical analyses will be presented separately for the HRA subgroups.

- Previous treatment with Disease Modifying Drugs (DMDs):
 - DMD pre-treated: Subjects will be categorized as DMD pre-treated if they have taken DMDs any time before start of study medication. Details of the definition of DMDs are specified in Appendix 1 (Section 18.1).
 - Pre-treatment naïve: all subjects not classified as DMD pre-treated.

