11.2 Other Baseline Characteristics

11.3 Demographics

Demographic characteristics will be summarized using the following information from the Screening/Baseline Visit CRF pages.

Demographic characteristics:

- Gender:
 - Male,
 - Female,
 - Missing.
- Race:
 - White,
 - Black or African American,
 - Asian,
 - American Indian or Alaska Native,
 - Native Hawaiian or Other Pacific Islander,
 - Other,
 - Not collected at this site,
 - Missing.
- Ethnicity Hispanic or Latino:
 - Yes,
 - No,
 - Missing.
- Ethnicity Japanese:
 - Yes,
 - No,
 - Missing.

- Age (years)
- Age categories:
 - ≤ 40 years,
 - 40 years, < 65 years,
 - ≥ 65 years,
 - Missing.
- Region:
 - Eastern & Central Europe: Austria, Germany, Hungary, Poland, Czech Republic
 - Scandinavia: Finland, Sweden
 - Mediterranea: Italy, Spain
 - Western Europe: France, United Kingdom
 - Australia,
 - Canada,
 - Israel.
- Country
 - Country 1
 - ...
- Pooled Centers

The following subject data listing will be provided:

- Demographic Data (Country, Sex, Race, Age, EDSS at Baseline, Number of relapses within 12 months prior to Baseline).

MS Disease Characteristics

The duration since onset and diagnosis of MS at Baseline in months, as well as the EDSS at Baseline, will be presented. In addition, the number of subjects grouped by the major systems affected (at onset of MS) will be presented.

- Time since onset of MS (months) = (Visit start date of Baseline Visit - date of first symptom + 1) / 30.4375,
- Time since diagnosis (months) = (Visit start date of Baseline Visit - date of diagnosis + 1) / 30.4375,
- Time since first relapse (months) = (Visit start date of Baseline Visit - date of first relapse + 1) / 30.4375,

- Number of previous DMDs (i.e., number of different PTs of DMDs as entered into the “Relevant Previous Medication Form” (see Appendix 1)),
 - 0
 - 1
 - 2
 - >2
- EDSS at Baseline,
- EDSS at Baseline,
 - ≤ 3
 - > 3
 - Missing
- Number of historical relapses within 12 months prior to Baseline (i.e., number of relapses from the “MS Relapse History Baseline” eCRF page):
 - Baseline Visit Start Date \geq onset date \geq Baseline Visit Start Date - 396 Days, if the day of the onset is available,
 - Month of the Baseline Visit Start Date \geq onset month \geq month of Baseline Visit Start Date – 13 months, if only the month of onset is available.
- Number of historical relapses within 12 months prior to Baseline categorized to:
 - 0
 - 1
 - 2
 - >2
- High-relapse activity (HRA)
 - Yes
 - No

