Note: While standardized lesion count is used in the 6-month IA, the annualized lesion count is used in the final analysis.

Vital Signs

The following Baseline characteristics will be provided in summary tables:

- Height, weight, body surface area, body mass index
- Body temperature, heart rate, Systolic Blood Pressure, Diastolic Blood Pressure

The body surface area (BSA) and body mass index (BMI) will be calculated with the following equations:

- $BSA(m^2) = ([height(cm) * weight(kg)] / 3600) ^ 0.5$
- $BMI (kg/m^2) = [weight (kg) / height (cm)^2] * 10000$

12 Previous or Concomitant Medications/Procedures

Concomitant medications are medications, other than study medications, which are taken by subjects during the study.

Concomitant medications will be summarized from the “Concomitant medication” eCRF page. ATC-1st level and preferred term will be tabulated as given from the WHO-DD dictionary current version. In case multiple ATC’s are assigned to a drug, all ATC-1st level will be used for reporting. All medications entered into the “Concomitant medication” eCRF page will be assumed to be “concomitant” irrespective of the actual start and end dates. In addition, all concomitant medications as well as concomitant medications given for disease related conditions will be presented by PT and by decreasing frequency.

Relevant previous medications are medications, other than study medications, which stopped before enrolment (i.e. date of informed consent [IC]). DMDs (see Section 8.2) administered between IC and start of study medication are major PDs that will be reported as relevant previous medications as well.

Relevant previous medications will be summarized from the “Relevant previous medication details” eCRF page. ATC-1st level and preferred term will be tabulated as given from the WHO-DD dictionary current version. In case multiple ATC’s are assigned to a drug, all ATC-1st level will be used for reporting. All medications entered into the “Relevant previous medication details” eCRF page will be assumed to be “previous” irrespective of the actual start and end dates. In addition, all relevant previous medications and relevant previous medications given for disease related conditions will be presented by PT and decreasing frequency.

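### SAP Appendix 1 and the count of previous DMDs by preferred term can misclassify prior DMD use

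*SAP*

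**What the plan says.** SAP Section 11.3, under MS disease characteristics, defines a baseline variable as "Number of previous DMDs (i.e., number of different PTs of DMDs as entered into the" previous-medication form. It is grouped as 0, 1, 2 and more than 2, with a pointer to Appendix 1.

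SAP Section 8.2 defines the subgroup: "Subjects will be categorized as DMD pre-treated if they have taken DMDs any time before start of study medication". Everyone else is naive, and Appendix 1 (Section 18.1) decides what a DMD is.

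Appendix 1 has a drug-name column and a PT column. The off-label row names "Off-label immunosuppressants (azathioprine, mycophenolate, cyclophosphamide" on the left and lists "AZATHIOPRINE CYCLOPHOSPHAMIDE METHOTREXATE" on the right. The row "Mitoxantrone (Novantrone" carries no star, and the footnote reads: "DMDs marked with a * are second line DMDs, which are not allowed as a previous medication according to the study protocol". Protocol Section 5.3.2, criterion 1, excludes "Previous exposure to drugs such as fingolimod, natalizumab, alemtuzumab, mitoxantrone and ocrelizumab".

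SAP Section 12 separately plans that "relevant previous medications given for disease related conditions will be presented by PT", so disease-related use is already distinguished elsewhere in the plan.

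**The concern.** One list serves three purposes: the number of previous DMDs, the pre-treated/naive split, and the prior-DMD and washout tables in SAP Section 12. If its two columns disagree, or if PTs stand in for drugs, these outputs can contradict each other for the same subject.

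The split is used in the sensitivity analyses of the primary endpoint (Section 14.1.2) and in the tertiary analyses of combined unique active (CUA), T1 gadolinium-enhancing and active T2 lesions (Sections 14.3.1 to 14.3.3 and 14.3.7). The count tells readers how treatment-experienced the population was.

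**Working it through.** The plan states no figure to reproduce. The check compares the list with itself, with the counting rule and with the protocol.

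**1. PTs against drugs.** Appendix 1 has 14 rows and 32 PTs. Seven rows hold more than one PT:

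| Row | PTs | Same drug under several terms? |
|---|---|---|
| Glatiramer | 2 | Yes: GLATIRAMER, GLATIRAMER ACETATE |
| Fingolimod | 2 | Yes: base and hydrochloride |
| Mitoxantrone | 2 | Yes: base and hydrochloride |
| Immunoglobulins | 3 | Yes: overlapping generic terms |
| Interferon beta | 6 | Partly: INTERFERON, INTERFERON BETA and PEGINTERFERON overlap the specific terms |
| Investigational | 7 | No: mostly different drugs, plus generic terms |
| Off-label | 3 | No: different drugs |

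Under the literal rule, a subject with two glatiramer records coded differently has 1 + 1 = 2 previous DMDs and moves from category 1 to category 2. With one other drug as well, the count is 3 instead of 2, which moves the subject from 2 to the top category. One interferon beta-1a product coded as INTERFERON, INTERFERON BETA and INTERFERON BETA-1A would reach 3 by itself. Exclusion 1 names fingolimod and mitoxantrone, so those pairs matter only for subjects enrolled against it. Glatiramer, interferon and immunoglobulins are the practical cases.

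**2. Names against PTs in the off-label row.**
- Named: azathioprine, mycophenolate, cyclophosphamide.
- PTs: azathioprine, cyclophosphamide, methotrexate.
- Named without a PT: mycophenolate. PT without a name: methotrexate.

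A mycophenolate-only subject is pre-treated if the name column governs and naive if the PT column does. The count follows PTs, so it could show 0 DMDs for a subject whom the subgroup table calls pre-treated.

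**3. Indication.** Neither Section 8.2 nor Appendix 1 requires use for MS. INTERFERON, PEGINTERFERON, the immunoglobulin terms, METHOTREXATE, OTHER ANTINEOPLASTIC AGENTS and INVESTIGATIONAL DRUG are not specific to it. Use of any of them for another disease, at any time before the first dose, makes a subject pre-treated.

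**4. Stars against Exclusion 1.** The criterion names five drugs. Four are starred and mitoxantrone is not. Daclizumab, siponimod and the investigational group are starred but not named, which the criterion's open wording can cover. Open wording cannot explain a missing star on a drug that is named.

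**Scale, by assumption only.** The planned size is 265. If 30% to 70% are pre-treated, the naive group is 265 × 0.7 ≈ 186 down to 265 × 0.3 ≈ 80. For k mycophenolate-only subjects labelled naive, the share of that group is k / n:
- k = 1: 1/186 = 0.5% to 1/80 = 1.3%
- k = 5: 5/186 = 2.7% to 5/80 = 6.3%

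Item 3 works in the opposite direction: it moves subjects out of the naive group, so the two cannot be added.

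**The case against.** The best defence is that these are editorial gaps with little consequence. Much of it stands.

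- A reader might infer that everything is applied by PT alone. Only the count says so. The appendix's subgroup sentence refers to drugs on the list, and mycophenolate is in the name column. The naive label arises only if the PT column is programmed. Medical review may also extend the list, although that clause does not say which column governs for a drug already named.
- A reader might infer that a prohibited-drug flag fails for mitoxantrone. No SAP output is derived from the star. Section 8.1 places major deviations in a separate specification, and Section 9 leaves deviations out of the analyses except for MRI under steroids. Mitoxantrone remains a listed DMD with PTs, so neither subgroup nor count changes.
- A reader might infer a weakened comparison between pre-treated and naive subjects. The SAP repeats analyses within subgroups and plans no such contrast, so the shares above describe group composition only.
- Interferon beta-1a, beta-1b and peginterferon beta-1a are separate products, and counting a switch between them as two is defensible.
- Counting exposure whatever its indication could be a deliberate choice, and the content of the previous-medication page is not in the documents. The SAP gives no reason for that choice, however, and Section 12 implies that disease-related use can be identified.

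The PT-based count, the mismatch in the off-label row and the unmatched star remain on the page.

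**Conclusion.** The point holds as a risk of misclassification. The documents do not show that any output is wrong, because that needs affected subjects and none are reported; the shares above rest on assumed numbers.

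The reach is limited to the baseline DMD count, the prior-DMD and washout tables, and the DMD-subgroup analyses. Among the MRI sections (14.3.1 to 14.3.11), only four use the split. The confirmatory test on the full analysis set does not use the list. The count is descriptive and enters no specified model.

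The primary-endpoint subgroup results already exist: Section 6.1 places all planned sensitivity analyses in the 6-month analysis, and Section 7 records decisions made after the primary analysis. A correction can still shape the final tertiary outputs. For the completed ones it can only be checked and documented.

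**What to change.** 1. In Section 11.3, count distinct active substances, with synonymous and salt-form PTs collapsed. Count an unspecific interferon term only where the subject has no specific term for the same product. Counting table rows would not do, because the off-label row holds different drugs.
2. In the off-label row, add the mycophenolate PTs, name methotrexate if it is meant to count, and state which column governs.
3. Restrict the PTs not specific to MS to records with a disease-related indication, using the distinction already made in Section 12.
4. Reconcile the mitoxantrone row and footnote with Exclusion 1.
5. Apply these changes before the final analysis. List any subject whose class changes in the completed 6-month subgroup outputs, or state that none does, and label any rerun as post hoc.

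The cost is an edit to the appendix, one line in Section 11.3, one sentence on indication and a reclassification check. No new data are needed, provided the indication behind the Section 12 tables is held for these records.
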